#### 4.1.5 Multicenter studies

Individual center results will not be displayed.

#### 4.1.6 Center pooling strategy

The data from all sites will be pooled for analyses purposes.

#### 4.1.7 Intercurrent event handling

ithorization As per protocol, if a study participant becomes no longer eligible for self-administration during the Self-administration Periods, he/she can continue to be treated on-site per protocol based on investigator decision. Adverse events, concomitant medication, vital signs, ECG, suicidality, blood and urine samples for safety laboratory tests, pregnancy tests, and IgG will continue to be collected from these study participants until End of Study Visit/Early Withdrawal Visit.

Stopping self-administration during the Self-administration Periods will be considered as an intercurrent event in the analysis.

For the primary and secondary endpoints focusing on the self-administration, all data collected after stopping the self-administration will not be included in the analysis of the primary and secondary endpoint.

For the safety analysis, all data collected after stopping the self-administration will be included in the analysis (treatment policy strategy). It will be assumed that the planned use of manual push or syringe driver will follow the initial schedule. The following endpoints will also be analysed including the data collected after stopping Self-administration:

- Total IgG level over time during the Training Period and Self-administration Periods.
- Occurrence of TEAEs leading to permanent withdrawal of rozanolixizumab during the study.

#### Handling of missing or partially missing dates 4.1.8

Partially or completely missing dates may be imputed for the following reasons:

- Classification of AEs as TEAEs;
- Classification of TEAEs into the study periods.
- Classification of medications as prior, or concomitant medications;
- Durations of AEs.

Imputed dates will not be shown in listings. All dates will be displayed as reported in the database.

The following rules will be applied for partially or completely missing start dates:

If year, month and day are all missing then assign the date of first dose of IMP. If an imputed start date is after the specified end date, then assign January 01 of the year of the end date, or

the date of screening if this is later (if the latter imputation results in an end date that is earlier than the start date, then use January 01).

- If month and day are missing, and year is:
  - the same as the year of the first dose of IMP then assign the month-day of first dose of IMP. If the imputed start date is after the specified end date, then assign January 01, or the month-day of screening date if this is later (if the latter imputation results in an end date that is earlier than the start date, then assign January 01);
  - not the same as the year of the first dose of IMP then assign January 01.
- If only day is missing, and month-year is:
  - the same as the month-year of the first dose of IMP then assign the day of first dose of IMP. If the imputed start date is after the specified end date, then assign first day of the month, or the day of screening date if this is later (if the latter imputation results in an end date that is earlier than the start date, then assign first day of the month);
  - not the same as the month-year of the first dose of IMP then assign the first day of the month.

The following rules will be applied for partially or completely missing stop dates:

- If only the month and year are specified, then use the last day of the month. If an imputed stop date is after last contact date and last contact date is before the data cut-off date, then assign last contact date as the stop date. If an imputed stop date is after last contact date and last contact date is after the data cutoff date, then assign data cutoff date as the stop date.
- If only the year is specified, then use December 31 of the known year. If an imputed stop date is after last contact date and last contact date is before the data cutoff date, then assign last contact date as the stop date. If an imputed stop date is after last contact date and last contact date is after the data cutoff date, then assign data cut-off date as the stop date.
- If the stop date is completely unknown, then use discharge date or data cut-off date. Discharge date refers to the date of the end of study visit for completed participants or the date of discontinuation for participants that were withdrawn. For any AEs with known start date after the date of discontinuation, the date of last contact will be used as the discharge date. For participants still ongoing in the study at the time of the data cut-off, and for whom no discharge date is available, the date of the data cut-off will be used instead of the discharge date.

Any medication with a start date on the first dosing date will be assumed to be concomitant.

Each TEAE should be classified into exactly one study period for the classification of TEAEs into study periods except if doubt remains after imputing the dates. In that case, an AE will be considered as TEAE in each study period.

Imputed AE dates will be used for the calculation of duration of AEs as described in Table 4–1.

Data availability	Onset date	Outcome date	Calculation rules
Complete data	D1	D2	Duration = D2 - D1 + 1 d
Start date partially or completely missing		D2	Duration $\leq D2 - D0 + 1 d$ Notes: D0 is imputed start date per above rules.
End date partially or completely missing	D1		For ongoing AE: Duration $\geq$ D3 – D1 d For resolved AE: Duration $\leq$ D3 – D1 d Notes: D3 is imputed end date per above rules.
Start and end date partially or completely missing			For ongoing AE: Duration $\geq$ D3 – D0 d For resolved AE: Duration $\leq$ D3 – D0 d Notes: D0 is imputed start date and D3 is imputed end date per above rules.

Table 4–1. Calculation rules for duration of AES	Table 4–1:	Calculation rules for duration of AEs
--	------------	---------------------------------------

Note: '--' represents a missing value

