- ^m In addition to a brief physical examination, a full neurological examination should be performed for any study participant who experiences severe and/or serious headache and for any study participant who experiences features suggestive of aseptic meningitis (see Appendix 14 [Section 10.14]). For details of the assessments included in these examinations, see Section 8.2.5. For additional assessments that may be required in case of these AESM, see Section 1.3.1 (Table 1-4).
- ⁿ Single 12-lead ECGs, which will be read locally.
- ^o Return of used and unused vials as well as all equipment and ancillary materials used for IMP administration.
- P The timing between Screening and the Baseline Visit needs to be a minimum of 14 days to confirm eligibility and to ensure all prerequisites are met.
- ^q Not applicable for study participants not considered eligible for self-administration, who will continue receiving IMP administered by the HCP at the study site (for additional details, see Section 4.1).
- ¹ Exploratory biomarker samples will be taken predose at Baseline (Day 1) for all study participants. In study participants who experience severe and/or serious headaches or features suggestive of aseptic meningitis, samples should also be collected 4 hours after the onset of the event, or otherwise as soon as possible within 72 hours after the onset of the event. For additional assessments that may be required in case of these AESM, see Section 1.3.1 (Table 1-4).
- ^s Participants completing all Treatment Periods, including the EOT Visit, and moving on to either a post-trial access program or commercially available rozanolixizumab during the SFU Period must undergo an earlier EOS Visit prior to this move (see Section 4.4 and Section 6.8).

Confidential Page 23 of 124

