6.7 Appendix 7: Prior / concomitant medications
6.7.1 Categorization

Medications will be classified as follows based on imputed start and stop dates & times outlined in Section 4.1.8.

- Prior medications will include any medications that started before the first administration of IMP.
- **Concomitant** medications will include any medications that have been taken at least once after the first administration of IMP during the Training/Self-administration/Follow-up Periods.

Among concomitant medications, medications will also be classified as part of Selfadministration Period 1 or Period 2.

The following rules will be used to assign a concomitant medication to Self-administration Period 1 or Period 2:

- Self-administration Period 1: a medication will be assigned to Self-administration Period 1 if it has been taken at least once between the first administration of IMP in Self-administration Period 1 (Visit 8) and 1 day before the first administration of IMP in Self-administration Period 2 (Visit 14). This includes medications that started prior to Self-administration Period 1 and those that continued into Self-administration Period 2.
- Self-administration Period 2: a medication will be assigned to Self-administration Period 2 if it has been taken at least once between the first administration of IMP in Self-administration Period 2 (Visit 14) and up to the end of Visit 20 assessments (EOT date).

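### Under SAP 4.1.8 and 6.7.1, a continuing medication with an unknown start date loses its prior flag even when it was recorded at Screening, so the prior-medication table is biased downward

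*SAP*

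**What the plan says.** SAP 4.1.8 lists the purposes for which dates are imputed. Besides the handling of adverse events, the list includes "Classification of medications as prior, or concomitant medications". The start-date rules that follow are common to all of these purposes:

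- Nothing known: "If year, month and day are all missing then assign the date of first dose of IMP".
- Only the year known, or only the month and year, and it matches the first dose: the start is set to the first-dose date.
- Only the year known and it differs: "not the same as the year of the first dose of IMP then assign January 01". A differing month and year goes to the first of that month.
- Fallback for a wholly missing start: "If an imputed start date is after the specified end date, then assign January 01 of the year of the end date, or" the screening date if that is later. Similar fallbacks exist for the partial-date cases.

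For stop dates: "If the stop date is completely unknown, then use discharge date or data cut-off date". The section adds: "Any medication with a start date on the first dosing date will be assumed to be concomitant".

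SAP 6.7.1 classifies on these imputed dates: "Prior medications will include any medications that started before the first administration of IMP". Concomitant status needs only some use after first dose, so the two classes can overlap. SAP 6.7.2 plans summaries of prior and concomitant medications on the Safety Set, and of concomitant medications on the Randomized Safety Set by period and method.

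The protocol's Schedule of Activities (Section 1.3) collects prior and concomitant medications from Screening onward. Its footnote p adds: "The timing between Screening and the Baseline Visit needs to be a minimum of 14 days".

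**The concern.** For adverse events, moving an unknown start to first dose is the cautious choice, because the event becomes treatment-emergent. For the prior flag, the same step has no such rationale. It gives the drug a start that is by definition not before first dose, and the prior flag is lost.

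Where the drug was already in use at Screening, the study's own record contradicts that date. Two participants on the same long-term therapy would then be classed differently only because one could supply a start date. At stake is a descriptive account of treatment received before the first dose. The baseline characteristics and demographics in SAP 6.4 contain no item for gMG therapy, so this account comes from the medication tables.

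**Working it through.** The plan states no figure on this point that could be reproduced. The check was to apply the rules of SAP 4.1.8 and 6.7.1 literally to a set of date patterns.

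**Inputs.** The rules are those set out above. The dates are illustrative assumptions: Screening 25 May 2023, first dose 15 June 2023, end of study and last contact 20 November 2023. The gap from Screening to first dose is 21 days, which meets the 14-day minimum.

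**Classification.** Prior if imputed start < first dose. Concomitant if imputed stop ≥ first dose.

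| Pattern | Recorded start | Recorded stop | Imputed start | Prior | Concomitant |
|---|---|---|---|---|---|
| a | none | ongoing or unknown | 15 Jun 2023 | no | yes |
| b | none | 1 Sep 2023 | 15 Jun 2023 | no | yes |
| c | none | 1 Jun 2023 | 25 May 2023 | yes | no |
| d | none | 1 Mar 2023 | 1 Jan 2023 | yes | no |
| e | none | 1 Mar 2021 | 1 Jan 2021 | yes | no |
| f | none | 2023 only | 15 Jun 2023 | no | yes |
| g | 2015 only | ongoing | 1 Jan 2015 | yes | yes |
| h | 2023 only | ongoing | 15 Jun 2023 | no | yes |
| i | Apr 2023 | ongoing | 1 Apr 2023 | yes | yes |
| j | Jun 2023 | ongoing | 15 Jun 2023 | no | yes |
| k | 1 Feb 2015 | ongoing | 1 Feb 2015 | yes | yes |

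**Results.**

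1. Five of the 11 patterns (a, b, f, h, j) lose the prior flag. These are chosen patterns, so five of 11 is not an estimate of frequency.
2. In all five the drug is still concomitant. No pattern drops a drug from both classes.
3. The fallback works only where a recorded end date precedes first dose (c, d, e). A continuing drug has no such end date, so the fallback does not reach pattern a.
4. A known earlier year (g) or earlier month and year (i) keeps the prior flag.
5. Patterns a and k can be the same long-term drug and differ only in whether the start was recorded.
6. If the recorded parts of the dates are correct, no start rule makes a drug begun after first dose prior. The error in the prior count therefore runs one way, downward.
7. If both dates are unknown and the drug in fact stopped before first dose, pattern a also adds a false concomitant record.

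**The case against.** The strongest reply is that little is lost. Concomitant status does not depend on the start date, so a continuing corticosteroid, cholinesterase inhibitor or immunosuppressant stays in the concomitant tables. Listings show dates as reported, so a missing start remains visible. The SAP states openly how it treats a start on the first dosing date. All of this stands, and it limits the point to one descriptive class.

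It also rules out two stronger readings. A reader might infer that background treatment as a whole is under-counted. The documents do not support that, because the drug remains counted as concomitant. A reader might also infer that the prior table is the one summary of therapy in use at entry. It is not: the definition of prior asks only that the drug started before first dose, so the table mixes stopped drugs with continuing ones even when every date is complete.

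Two further objections stand in part. In patterns h and j the recorded start is recent, and whether it fell before or after first dose can be truly uncertain; the rule is contradicted only where a Screening or Baseline record settles the matter. Also, the schedule has a single medication row running across visits, and the documents do not say whether each record keeps the visit at which it was first entered. That is a condition on the fix. It does not defend the rule.

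**Conclusion.** The point holds in a limited form. A medication with a wholly missing start date, or with only the first-dose year or first-dose month and year known, and not known to have ended before first dose, is classed as concomitant but not prior, even when the Screening record shows earlier use. The prior-medication count is biased downward.

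The size cannot be computed, because the documents do not say how many medication records lack a start date. A reader might be tempted to supply one. If 60% of participants used a class at entry and 5% to 20% of those records were affected, the table would show 60% × 0.95 = 57% down to 60% × 0.80 = 48%. Neither input is in the documents. The sum also assumes that no affected participant has another, properly dated record in the same class, since SAP 6.7.2 counts participants. It should not be read as an estimate.

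The conclusion rests on a literal reading of the rules and on prior medications being tabulated separately from concomitant ones; SAP 6.7.2 does not give the table layout. No primary or secondary endpoint uses the classification.

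**What to change.** Add one sentence to SAP 4.1.8 or 6.7.1, for example: *A medication recorded at Screening, or recorded at Baseline as taken before the first dose, is classed as prior whatever its imputed start date, and is also classed as concomitant if it continued after the first dose.*

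Keep the existing start-date imputation for all other purposes, including the assignment of medications to Self-administration Periods 1 and 2, which relies on imputed dates. Two broader changes are best avoided. Restricting the imputation to adverse events would leave medications without the dates needed for period assignment. Treating every incompletely dated medication as prior by default would mislabel some drugs begun during the study.

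The cost is a small change to the medication derivation. It needs the record to show that the drug was reported before first dose, so the sponsor should confirm that the CRF data carry this information.

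### SAP Table 4-1 sets the upper limit on duration one day too short for resolved adverse events whose stop date is imputed

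*SAP*

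**What the plan says.** Table 4-1 in SAP Section 4.1.8 has four rows, according to which AE dates are complete.

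- Both dates known: "Duration = D2 - D1 + 1 d".
- Start imputed (D0), stop known (D2): at most D2 - D0 + 1 days.
- Start known, stop imputed (D3): "For ongoing AE: Duration $\geq$ D3 – D1 d" and "For resolved AE: Duration $\leq$ D3 – D1 d".
- Both imputed: at least D3 - D0 days if ongoing; if resolved, "For resolved AE: Duration $\leq$ D3 – D0 d".

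The extra day is present in both rows with a known stop date and absent from all four expressions that use D3. No reason is given.

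The same section defines D3. With the day missing: "If only the month and year are specified, then use the last day of the month". With day and month missing: "If only the year is specified, then use December 31 of the known year". In both cases D3 is capped at last contact or data cut-off. With nothing known: "If the stop date is completely unknown, then use discharge date or data cut-off date".

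SAP Section 4.5.2 puts AE duration in the listings. Section 4.1.8 keeps imputed dates out of them.

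**The concern.** The resolved-AE rule is written as an upper limit, so it should hold for every stop date compatible with what was recorded. D3 is chosen as the latest such date. If the event did stop on D3, the complete-data row gives a duration one day above the limit. The table then contradicts itself for the very date it imputes.

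At stake is the accuracy of a derived value in the AE listings. The reader of a listing sees the partial stop date and the limit but not D3, and so cannot easily see where a limit of 0 days came from. Elsewhere the SAP counts inclusively: study medication duration (Section 4.5.1) and MG duration (Section 6.4) both add 1 day.

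**Working it through.** **Inputs.** The four rows of Table 4-1 and the stop-date and start-date imputation rules, all from SAP Section 4.1.8. The calendar dates below are illustrative.

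**Definition of duration.** The complete-data row gives D2 - D1 + 1. An AE that starts and stops on 30 June lasts 30 - 30 + 1 = 1 day.

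**Resolved AE, onset known, stop recorded only as June.** D3 = 30 June.

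| Onset | Limit as written, D3 - D1 | Duration if it stopped on D3, D3 - D1 + 1 |
|---|---|---|
| 10 June | 30 - 10 = 20 d | 21 d |
| 30 June | 30 - 30 = 0 d | 1 d (the only possible value) |

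The gap is (D3 - D1 + 1) - (D3 - D1) = 1 day for every onset.

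**How often the limit fails.** In a 30-day month there are 30 × 31 / 2 = 465 pairs of onset day and true stop day. The limit as written fails when the stop day is D3, which is one pair per onset day, or 30 of 465. With 1 day added it fails in 0 of 465. These are counts of possibilities, not an expected frequency in the trial.

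**Ongoing AE, onset known.** With onset 10 June and D3 = 30 June, the table says at least 20 days; the inclusive count is at least 21. The lower limit of 20 is looser by a day but true.

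**Ongoing AE, both dates missing.** Let S be the true start. The inclusive duration up to D3 is D3 - S + 1.

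- As written, D3 - D0 is a true lower limit when S is no later than D0 + 1.
- With 1 day added, the limit is true only when S is no later than D0.

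So the extra day loses the case S = D0 + 1 and gains none. Take a start recorded only as May, in a month other than that of first dose, so that D0 = 1 May, and let D3 = 30 June. Then D3 - D0 = 30 + 30 = 60. If the true start is 2 May, the duration to D3 is 59 + 1 = 60 days. At least 60 is true; at least 61 is false.

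**Resolved AE, both dates missing.** Adding 1 day makes the upper limit D3 - D0 hold more often, but not always. Section 4.1.8 sets D0 to the first-dose date when the start is wholly missing, or when the known part of it matches the first-dose date. That need not be the earliest possible start. For example, with first dose on 12 June, start recorded as June and D3 = 30 June, the corrected limit is 30 - 12 + 1 = 19 days. An event that ran from 3 June to 30 June lasted 28.

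**The case against.** The strongest reply is that Table 4-1 only gives approximate limits from imputed dates, and that one day in a listing is immaterial. Part of this stands. With a known onset, the resolved limit fails only if the event ended exactly on D3, and the 0-day value needs D3 = D1. Limits that involve D0 are approximate anyway, including the start-imputed row that already has the extra day. But for a known onset there is no D0. The limit is meant to be exact there, and a maximum of 0 days is impossible under the SAP's own count.

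Three stronger readings are tempting, and the documents do not support them.

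- **All four D3 expressions are wrong.** The ongoing limit with known onset is valid as it stands, and the ongoing limit with both dates missing would be made worse by the extra day.
- **Safety endpoints are affected.** The primary endpoint is successful self-administration (SAP Section 4.2.1). The secondary endpoints are occurrences, summarized as numbers and proportions of participants (Sections 4.3.1.1 and 4.3.2). Periods are assigned by start date. None of these uses duration.
- **Short events such as infusion-site reactions or headache will often be listed as 0 days.** The documents say nothing on how long such events last or how many AEs have partial stop dates. The 24-hour window for local site reactions concerns when they occur after dosing, not their length.

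**Conclusion.** The table is wrong as written for resolved AEs with a known onset and a partial or missing stop date: the stated maximum is one day short, and it reads 0 days when onset falls on D3. The resolved cell with both dates missing has the same omission, on top of the approximation in D0. This is a minor error confined to AE listings.

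The conclusion assumes that the inclusive count in the complete-data row is the intended definition of duration, and that for a resolved AE D3 is the latest admissible stop date, as the imputation rules imply. The number of listed values affected cannot be stated, because the documents do not say how many stop dates are incomplete.

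**What to change.** In Table 4-1, change the two resolved-AE expressions:

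- start known, stop imputed: Duration ≤ D3 - D1 + 1 d;
- both imputed: Duration ≤ D3 - D0 + 1 d, with a note that this limit stays approximate because D0 can be the first-dose date.

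Leave the ongoing expression with both dates missing unchanged. In the ongoing expression with known start, adding 1 day is optional and serves only consistency.

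The cost is two cells of one table and the matching derivation for the listings, three if the optional change is made. No new data are needed and no summary table changes.

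### SAP Table 4-1 gives ongoing AEs with an incomplete start date a minimum duration counted from an early-imputed start, which is not a valid lower limit

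*SAP*

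**What the plan says.** SAP 4.1.8 imputes incomplete AE dates, among other reasons to calculate AE durations.

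**Start date (D0)**
- Only the day missing, month differs from the first-dose month: "not the same as the month-year of the first dose of IMP then assign the first day of the month".
- Only the day missing, first-dose month: "the same as the month-year of the first dose of IMP then assign the day of first dose of IMP".
- Month and day missing, year differs from the first-dose year: "not the same as the year of the first dose of IMP then assign January 01". If the year is the first-dose year, the month and day of first dose are used.
- Nothing known: "If year, month and day are all missing then assign the date of first dose of IMP".

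**Stop date (D3).** An ongoing AE has no stop date, so this rule applies: "If the stop date is completely unknown, then use discharge date or data cut-off date". For a participant who completed the study, the discharge date is the End of Study visit.

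**Duration (Table 4-1)**
- Start incomplete, end known (second row): at most D2 − D0 + 1.
- Start known, end incomplete (third row): at least D3 − D1 if ongoing.
- Both incomplete (last row): "For ongoing AE: Duration $\geq$ D3 – D0 d", with the note that "D0 is imputed start date and D3 is imputed end date per above rules".

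SAP 4.5.2 puts AE duration in the AE listings. SAP 4.1.8 says that listings show dates as reported, without the imputed values.

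**The concern.** A lower limit on duration has to be counted from the latest start that the recorded parts allow. D0 is the earliest such start for a treatment-emergent AE, so counting from it gives the longest possible elapsed time. The at-least sign is sound in the third row because the onset D1 is known there. The last row keeps the sign but replaces D1 with the imputed D0. One early-imputed date cannot give an upper limit in the second row and a lower limit in the last.

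An ongoing AE has no stop date, so every ongoing AE with an incomplete start falls in the last row. The listing would then state a minimum duration that the data do not support. Because D0 is not displayed, the reader sees a partial start date beside that minimum without the date behind it.

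**Working it through.** The plan gives a rule and no figure, so there is nothing to reproduce. The check applies the rule and compares the result with the elapsed time.

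**Inputs**
- D0, D3 and the duration rule: SAP 4.1.8 and Table 4-1.
- Doses: SAP 1.2 places infusions at Visits 2 to 7, 8 to 13 and 14 to 19, which is 18 doses.
- Dose interval (assumption): weekly, because the visit days are redacted. The protocol's Schedule of Activities allows 5 to 9 days between doses.
- End of Study: 8 weeks (56 days) after the last dose.
- First dose (illustrative assumption): 11 September 2023. The SAP version history says that no Baseline visit preceded 5 May 2023, so the date is feasible.

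**Timeline.** The last dose is on Day 1 + 17 × 7 = Day 120. Visit 20 is on Day 127 (Week 19) and Visit 21 on Day 120 + 56 = Day 176 (Week 26). Both agree with the SAP's week labels. First dose to Visit 21 is 176 − 1 = 175 days, or 25 weeks. The same figure follows from 29 weeks in total less 4 weeks of screening. With first dose on 11 September 2023, D3 is 4 March 2024.

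**Formulas**, with t the true start:
- Printed minimum = D3 − D0.
- Elapsed at D3, inclusive = D3 − t + 1.
- Excess = (D3 − D0) − (D3 − t + 1) = t − D0 − 1.

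**Worked case.** True start 27 February 2024 (Day 170), so elapsed = 6 + 1 = 7 days.

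| Recorded start | D0 | Printed minimum | Elapsed | Ratio |
|---|---|---|---|---|
| Feb 2024 | 1 Feb 2024 | 32 d | 7 d | 4.6 |
| 2024 | 1 Jan 2024 | 63 d | 7 d | 9.0 |
| nothing | 11 Sep 2023 | 175 d | 7 d | 25.0 |

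For the first line, the latest start that fits the record is 29 February. A valid minimum is therefore 4 days by the table's D3-minus-start convention, or 5 days inclusive.

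**A milder case.** True start 7 February 2024 (Day 150), 27 days elapsed. The printed minimum is 32, 63 or 175 days, which is 1.2, 2.3 or 6.5 times the elapsed time.

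**Largest excess.** With only the day missing, t − D0 is at most 30 days in a 31-day month, so the excess is 29 or 30 days depending on whether the start day is counted. With nothing known, it approaches the full 175 days for an onset just before D3.

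**How often the printed minimum exceeds elapsed time.** The excess is positive when t is at least 2 days after D0, so only the first two start days after each possible D0 escape. Treatment-emergent start days 1 to 175 run from September to March.
- Day missing: seven calendar months, 175 − 7 × 2 = 161 of 175 (92%).
- Only the year known: two years, 175 − 2 × 2 = 171 of 175 (98%).
- Nothing known: 175 − 2 = 173 of 175 (99%).

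If the AE resolves 7 days after D3, the printed minimum still exceeds the total duration for 118, 157 and 166 of the 175 start days. These are counts of possible start days, not predictions of how many AEs will be affected.

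**The case against.** The strongest objection is that an ongoing AE has no known total duration at D3. A printed minimum that exceeds the elapsed time is still a true statement if the event goes on long enough afterwards. This stands. A reader might infer that every such listed minimum is false, or that it is several times the true duration. The documents do not support either reading, because the comparison available is with elapsed time at D3. What can be said is that D3 − D0 is not a valid lower limit: it bounds the total duration in neither direction.

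Second, D0 is not always the earliest possible start. AEs are collected from informed consent, and in several cases D0 is the first-dose date. An AE that began on 4 September 2023, recorded only as September 2023, gets D0 = 11 September. Its printed minimum is 175 days against 183 elapsed, so the statement holds. The point therefore concerns treatment-emergent AEs. The 1 January default also applies only when the recorded year differs from the first-dose year.

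Third, the large excesses are extremes. They need a late onset and a start date with little or nothing recorded, and the largest also needs full follow-up, which a move to post-trial or commercial drug can shorten. With only the day missing, the excess is often small: 94 days printed against 87 elapsed for an onset on 9 December 2023 in the same example. The documents do not indicate how many AEs will have incomplete starts.

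Fourth, the consequence is minor. The specified AE summaries use incidence, not duration, and the reported partial date stays visible. The error lengthens apparent durations, so it does not favour the product. All of this limits the size of the point. None of it makes the last row correct, and no other section amends it.

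**Conclusion.** The ongoing-AE rule in the last row of Table 4-1 is wrong as written. For a treatment-emergent AE with an incomplete start, D3 − D0 is about the maximum elapsed time at D3 and should not be printed as a minimum. The conclusion about direction follows from the SAP's own imputation rules and needs no outside assumption.

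The 25-week upper figure rests on weekly dosing and full follow-up, and the worked dates rest on the illustrative first dose. No primary or secondary endpoint and no planned summary table depends on the rule. This is a minor correction to the AE listings, worth making because the rule would otherwise print unsupported minimum durations.

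**What to change.** In the ongoing branch of the last row, replace D0 with the latest start compatible with the recorded parts: the last day of the recorded month, the last day of the recorded year, or D3 if nothing is known, in each case capped at D3. Alternatively, show the duration as not determined for these events.

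Use D0 only for the at-most limits, and add a note that those limits hold for AEs starting on or after first dose.

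The cost is one table cell and one extra derived date in the listing program. Data collection, endpoints and summary tables do not change.
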